3.2 Subject Compensation

Subjects will accrue compensation according to the below table. They will be handed a Walmart ® gift card of \$25 at the end of Visit 1. They will be handed a UAMS check for their Visit 2 compensation immediately after their participation in visit 2 ceases (whether completed or not). If they were to fully attend every visit, their total amount would be \$125. If they stop participating prior to the completion of study visit 2, they will receive prorated pay of \$20 per hour.

Visit	Amount

1	\$25 (gift card in hand)
2	\$100 (check)

3.3 Recruitment

Potential subjects will be recruited from the Little Rock and central Arkansas areas by use of flyer, social media, ARResearch.org registry, and word of mouth. Individuals interested in the study will be scheduled for Visit 1.

3.4 Study Registration

This study will be registered on clinicaltrials.gov website as required.

3.5 Sample Storage

Blood samples will be kept frozen at -80 degrees Centigrade or colder once the initial processing has taken place. Samples shall be stored in appropriate freezers in the PI's laboratory, located in a restricted area inside the UAMS IOA building. Said freezers are monitored continuously for proper temperature and working condition. All blood samples shall be identified using a unique study acronym. None of a subject's personal identifiers shall be present on any biological sample.

3.6 Retention of Samples for Future Use

With explicit permission via the consent form, plasma samples will be kept for future approved research.

- Samples will only be released to investigators within or outside of UAMS who provide proof of appropriate IRB review and/or approval.
- Samples will be kept in the PI's freezers located on the 7th floor of the UAMS Reynolds
 Institute on Aging. This floor is controlled-access via approved UAMS badges.
- All samples are labelled with an alpha-numeric code. The key to this code is kept on a secure UAMS server to which access is limited to study staff.
- No personal identifiers are on the samples.

Version #: 10 IRB# 262590
Date: 31May22 Page 11

 Samples will be kept for up to approximately 10 years, after which they will be placed into biohazard trash receptacles.

- Samples will be retained for further analyses related to metabolic biomarkers (e.g., metabolomics, proteomics, inflammation markers, etc.).
- Subjects can rescind their permission to keep their samples by contacting any of the study staff listed in the consent form.

4.0 Study Population

Up to 35 subjects will be enrolled in order to meet the goal of 10 completers in each of the three groups. Attempts will be made to balance sexes within groups.

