1.2 Previous research on the topic

The rate of loss of muscle with aging in any given individual is variable and may be influenced by genetic factors, level of activity, amount of protein in the diet, total body weight, and occurrence of serious diseases that directly affect muscle mass and function. Nonetheless, the estimate from cross-sectional data that between 0.5-1.0 % of muscle mass is lost per year after the age of 70 years is reasonable (3). The physiological basis for loss of muscle over time results from an imbalance between the rates of muscle protein synthesis and breakdown. Consumption of dietary protein results in the absorption of amino acids and the activation of protein synthetic processes throughout the body, particularly muscle protein synthesis (4). There is a direct relationship between the amount of dietary protein intake and the net gain in body protein in young healthy individuals (5). Anabolic resistance refers to the circumstance in which dietary protein has a diminished stimulatory effect on the net production of new muscle protein. Critical illness (6) or the response to a major burn injury (7) provide clear-cut examples of anabolic resistance. In anabolic resistance associated with these pathological conditions, the normal linear relationship between dietary protein intake and net protein synthesis is capped, meaning that beyond a certain level of protein intake there is no further gain in net protein balance. For example, beyond a level of protein intake of 1.1 g protein/kg/day there is no net gain in body protein in critically ill patients (6). Once the maximal rate of protein synthesis is reached, there is no further gain in net protein synthesis, as the rate of protein breakdown is not affected by dietary protein consumption in severely catabolic patients. The

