3.0 Study Design and Procedures

We will enroll up to 35 subjects with a goal to study up to 30 healthy male and females: a group of 10 whose age is between 18 and 30 years, a group of 10 whose age is 70-89 years without the presence of sarcopenia, and a group of 10 whose age is 70-89 years with sarcopenia. We will use a 5-hour (one hour prior and 4 hours post-consumption of an amino acid supplement) period to completely characterize the plasma amino acid response to 10 grams of free-form essential amino acids of which 10% of the leucine content has been enriched with L-[1-13C] leucine. The principal end-point will be plasma amino acid response over the 4 hours following the consumption of the study product.

Secondary endpoints include body composition and total body water measurements. Small shifts in fluid from the extracellular to intracellular space likely correspond with EAA appearance and disappearance in plasma. BIA is a non-invasive, rapid assessment that is sensitive to acute shifts in fluid that are associated with disease and malnutrition states, such

Version #: 10 IRB# 262590 Page 7

Date: 31May22

Institution: UAMS

Sponsor: UAMS/TRI

as sarcopenia. As an exploratory analysis, we will measure acute shifts in total body,

intracellular, and extracellular fluid using multifrequency BIA throughout visit 2. This will serve

as preliminary data on a potential non-invasive method to evaluate muscle quality, anabolic

resistance, and a proxy indicator of sarcopenia.

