4.1 Inclusion Criteria

Ages 18 – 30 and 70-89 yrs.

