7.0 Data Analysis

7.1 Statistical Analysis plan

Means by which experimental data will be analyzed or interpreted: Changes in the plasma amino acids area under the curve (AUC), maximal amino acid concentration, change from basal to maximal amino acid concentrations, rate to maximal amino acid concentration, and the clearance rate of amino acids from the plasma will be assessed with an one-way ANOVA with appropriate post hoc testing. Statistical significance will be accepted at an alpha level of p ≤ 0.05 .

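### Age is neither balanced nor adjusted for between the two older groups, so an age effect could be read as a sarcopenia effect; the size is uncertain

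*Combined protocol and SAP*

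**What the plan says.** Section 3.0 defines the two older groups over the same wide range. One is "a group of 10 whose age is 70-89 years without the presence of sarcopenia"; the sarcopenic group has the same age limits and the same size. The inclusion criterion in section 4.1 is "Ages 18 – 30 and 70-89 yrs", with no sub-bands. Section 7.4 assigns older subjects to a group by measured handgrip and lean tissue. Its numeric handgrip cut-offs differ by sex but not by age.

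Section 4.0 sets the numbers, "Up to 35 subjects will be enrolled in order to meet the goal of 10 completers in each of the three groups", and then gives the only balancing statement: "Attempts will be made to balance sexes within groups". Section 7.1 lists the amino acid measures, which "will be assessed with an one-way ANOVA with appropriate post hoc testing". It names no covariate. No section matches, stratifies or adjusts for age within the older groups.

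The background in section 1.2 accepts as reasonable that "between 0.5-1.0 % of muscle mass is lost per year after the age of 70 years".

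**The concern.** The hypotheses in section 2.0 say that sarcopenic elderly subjects differ from, and can be told apart from, both young and healthy elderly subjects. The comparison with the young group mixes age and sarcopenia by design. Only the comparison of the two older groups can separate them.

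Those groups are formed by measurement, not by randomisation, and muscle is one of the measurements. If muscle falls with age, selecting on low muscle also selects on age. If age also affects the plasma amino acid response by another route, the older-versus-older difference contains an age component that the planned ANOVA cannot remove. A positive result would then not show that the test detects sarcopenia.

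**Working it through.** **The plan's own sample size.** Section 7.2 gives 8 per group for d = 1.6, alpha 0.05 and 80% power. A two-sided two-sample t-test has power 78.5% at n = 7 and 84.5% at n = 8, so the figure reproduces. That d compares healthy young subjects with incipient sarcopenia, so it says nothing about the older-versus-older contrast.

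**Direction of the age gap.** At the section 1.2 rate, the loss between 70 and 89 is 0.5% × 19 = 9.5% to 1.0% × 19 = 19%. This compares the two ends of the range, not two group means.

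**Size of the age gap.** Assume ages uniform over 70-89, so SD = √((20² − 1)/12) = 5.77 years, and a between-person CV of muscle mass of 10-20% (not in the documents). The age-muscle correlation is ρ = rate × 5.77 / √((rate × 5.77)² + CV²). A median split on muscle gives a mean gap of roughly 2 × 0.798 × ρ × 5.77.

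- Rate 0.5%, CV 20%: ρ = 0.0288/0.202 = 0.143, gap 1.3 years.
- Rate 1.0%, CV 10%: ρ = 0.0577/0.1155 = 0.50, gap 4.6 years.

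Simulating uniform ages with a cut at the 20th or 50th percentile gives about 1.3 to 5 years. Chance adds to this. With no link between age and sarcopenia, the SE of the age difference is 5.77 × √(2/10) = 2.58 years, so a gap of at least 4 years arises in about 12% of samples.

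**False-positive rate.** Assume no sarcopenia effect, within-group age SD 5 years, and correlation r between age and response. The spurious effect is d = r × gap / 5. With 10 per group the noncentrality is d × √(10/2) = 2.236d, and the two-sided test on 18 df rejects beyond ±2.101. Sidedness is not stated in the plan; two-sided is assumed.

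| Gap (years) | r = 0.2 | r = 0.3 | r = 0.5 |
|---|---|---|---|
| 1 | d 0.04, 5.1% | d 0.06, 5.2% | d 0.10, 5.5% |
| 3 | d 0.12, 5.7% | d 0.18, 6.7% | d 0.30, 9.7% |
| 5 | d 0.20, 7.1% | d 0.30, 9.7% | d 0.50, 18.5% |

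With an age SD of 5.8 years instead, the 5-year row becomes 6.6%, 8.5% and 15.1%. If the unnamed post hoc test is Tukey's across three groups (assumed), simulation gives about 3% at gap 3, r = 0.3 and 7% at gap 5, r = 0.4, against 7% and 14% uncorrected. The correction lowers the rejection rate but leaves the bias in the estimated difference.

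**Cost of adjustment.** With 10 per group and age SD 5, the ratio of adjusted to unadjusted SE is about √{(1 − r²)[1 + (gap² + 5)/80]}. The 5 is the chance variance of the age difference (2 × 25/10). The 80 is 16 × 25/5, where 16 is 18 df less 2. At r = 0.3:

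- 3 years: √(0.91 × 1.175) = 1.03
- 5 years: √(0.91 × 1.375) = 1.12
- 8 years: √(0.91 × 1.8625) = 1.30

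Direct simulation gives increases of 3%, 11% and 29%, and the false-positive rate returns to about 5%.

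**The case against.** The strongest objection is that neither link in the chain is measured. Section 1.2 gives a cross-sectional average and says individual loss varies with genetics, activity, diet, weight and disease. The only numeric grouping thresholds are for handgrip, for which no rate of decline is given. The evidence on reduced responsiveness compares older with younger adults and concerns muscle protein synthesis, not plasma amino acids within 70-89. This stands, and it is why the size above is an assumed range.

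A second objection is that section 1.1 holds that the muscle response determines amino acid kinetics. If age acts mainly through muscle, little spurious effect remains, and adjusting for age may remove part of the real one. That also stands, and it is a reason to make the adjusted contrast supportive and not primary.

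A reader might infer more: that the sarcopenic group must be older by construction, by 3-8 years, with a false-positive rate near 40%. The documents do not support this. The 9.5-19% figure contrasts the ends of the age range. The section 1.2 rate with plausible variation between people gives about 1.3-5 years. A rate near 40% needs an 8-year gap and a correlation of 0.5 together, in an uncorrected two-group test.

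A reader might also infer that the older groups must be matched in age-by-sex cells. Up to 35 may be enrolled for 30 completers, which leaves five spare places. Under section 3.1, body composition may wait until Visit 2, so group may be unknown until the challenge day. Four cells in a group of 10 average 2.5 subjects. Compulsory matching is not clearly affordable.

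**Conclusion.** The point holds. Nothing in the plan balances or adjusts for age between the older groups, and the protocol's own muscle-loss figure predicts the direction of the imbalance. The contrast affected is the only one that can separate sarcopenia from age.

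The size is uncertain. Under the assumed gap of 1-5 years, age SD of 5 years and correlation of 0.2-0.5, the spurious effect is d = 0.04-0.50. The uncorrected false-positive rate is about 5-19% in place of the 5% implied by "Statistical significance will be accepted at an alpha level of p ≤ 0.05". At the low end the effect is negligible. At the high end it would weaken a claim that the test identifies sarcopenia. No age imbalance has been shown to exist; the plan simply has no means of dealing with one.

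**What to change.** In section 7.1, pre-specify a supportive contrast of sarcopenic with non-sarcopenic older subjects, with age as a continuous covariate, and report the age distribution by group. Age is already collected for eligibility, so this needs no new data or procedure and leaves the primary ANOVA unchanged. The price is precision if the groups turn out far apart in age: at a correlation of 0.3 the SE is about 3% higher at a 3-year gap, 11% at 5 years and 29% at 8 years.

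In section 4.0, extend the existing best-effort sentence from sex to sex and, across the two older groups, age, where this is feasible within the 35-subject cap. Age-by-sex cell matching should not be required. The cost is wording and possibly slower filling of one older group. A smaller gap also keeps the adjusted contrast precise.

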4.1 Inclusion Criteria

Ages 18 – 30 and 70-89 yrs.

4.2 Exclusion Criteria

- History of diabetes
- History of malignancy or chemo/radiation therapy in the 6 months prior to enrollment
- History of gastrointestinal bypass/reduction surgery (Lapband, gastric sleeve, etc.)
- Pregnant females
- Unwilling to wear the breath-collection mask
- Subjects who cannot refrain from using protein or amino acid supplements for 7 days prior to Visit 2
- Concomitant use of oral or injectable corticosteroids
- Concomitant use of testosterone, IGF-1, or similar anabolic agent
- Any other disease or condition that would place the subject at increased risk of harm if they
 were to participate, at the discretion of the study physician

5.0 Risks and Benefits

There are no direct benefits for the subjects. Expected risks associated with this protocol are

described in detail below. All experimental procedures will be performed by appropriately

trained and credentialed personnel.

5.1 Blood sampling:

Blood samples will be collected solely for the purpose of experimentation. The blood will be

used to measure plasma amino acid concentrations and possibly stable isotope enrichment,

glucose, and insulin. The total amount of blood taken will be approximately 60 mL. Subjects

should have no noticeable effects from this volume.

5.2 DEXA, In Body scans:

The DEXA scan exposes subjects to approximately ½ of the radiation of one chest x-ray.

Subjects will undergo 1 DEXA scan. The In Body scans do not pose any risks.

5.3 Physical and Functional Testing:

The primary risks are fatigue and muscle soreness.

5.4 Study supplement:

The test composition is a patented mixture of 10 grams of amino acids (total of 17.8 grams of

commercial product: XS Muscle Multiplier) dissolved into approximately 10 ounces of water. It

is a commercially available product manufactured by Prinova™ Solutions (Prinovausa.com).

All components of the composition have been ruled as Generally Regarded as Safe (GRAS)

by the FDA.

5.4.1 Conflict of Interest

UAMS and [name] are listed on the approved patent for this particular amino acid

supplement. There is an approved COI plan on file for [name]. He will not have access to

raw data, only a summary of the compiled data.

Version #: 10

IRB# 262590 Date: 31May22 Page 13

5.5 Stable Isotope Ingestion:

There are no known risks of ingestion of the stable isotope of leucine.

5.6 Confidentiality:

A potential risk is the loss of confidentiality. Measures to protect the confidentiality of study participants will be implemented as described in the Data Handling and Record keeping section below.

5.7 Breath Sampling

The only risk of breath sampling is potential claustrophobia and subsequent anxiety.

6.0 Data Handling and Recordkeeping

Source documents, paper questionnaires and consent forms, and CRFs will be stored in a secure area of the Pl's laboratory. Access will be limited to study personnel. Documents containing identifiers will be destroyed by shredding approximately 7 years after data analysis is completed or publication of data; whichever is longest. At no time shall Protected Health Information be released to non-study personnel.

The Principal Investigator will carefully monitor study procedures to protect the safety of research subjects, the quality of the data and the integrity of the study. All study subject material will be assigned a unique identifying code or number. The key to the code (the instrument associating the data with subject identity) will be kept on a password-protected UAMS server, located behind locked doors in a restricted access area of the UAMS campus. The code file will contain subject initials, sex, subject ID, enrollment data, and anthropometric data; it will not include any identifiers. Only those individuals listed on the title page of this protocol and their research staff members will have access to the code and information that identifies the subject in this study. This file will be deleted approximately 7 years after data analysis is completed.

7.0 Data Analysis

7.1 Statistical Analysis plan

Means by which experimental data will be analyzed or interpreted: Changes in the plasma amino acids area under the curve (AUC), maximal amino acid concentration, change from basal to maximal amino acid concentrations, rate to maximal amino acid concentration, and the clearance rate of amino acids from the plasma will be assessed with an one-way ANOVA with appropriate post hoc testing. Statistical significance will be accepted at an alpha level of p ≤ 0.05 .

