
Version #: 10 IRB# 262590 Page 6

Date: 31May22

and muscle protein synthesis has been demonstrated to be driven by the change in plasma essential amino acid concentrations (2). Stated another way, the changes in plasma essential amino acid concentrations following the ingestion of dietary protein drive the increase in muscle protein synthesis. The analogous parallel to amino acid and muscle is the use of the oral glucose tolerance test used to classify individuals with prediabetes and type-2 diabetes. Therefore, demonstrating that the essential amino acid response to an oral amino acid challenge can differentiate between elderly and young populations is a worthwhile first step in developing a new clinical diagnostic test to identify sarcopenia.

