2.0 Hypotheses

We hypothesize that plasma amino acid response will be altered in elderly sarcopenic adults as compared to young and elderly healthy subjects.

We also hypothesize that the pharmacokinetics of plasma amino acids can be used to distinguish sarcopenic elderly from young and elderly healthy.

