7.2 Sample Size Calculation & Power Analysis

Statistical power and sample size are based on previous studies investigating differences in plasma amino acids in younger and older adults following the ingestion of 10 grams of free form essential amino acids (12). For peak EAA concentrations previous studies have demonstrated an effect size (Cohen's D) of 1.6 between health young and individuals with incipient sarcopenia. This effect size indicates we need 8 individuals in each group to detect a significant difference at an alpha level of 0.05 with 80% power.

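### Five response parameters are each tested at 0.05 with none named primary, and the plan does not say whether the sarcopenic group must differ from both other groups

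*Combined protocol and SAP*

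**What the plan says.** - **End-point (3.0).** "The principal end-point will be plasma amino acid response over the 4 hours following the consumption of the study product". No summary parameter and no analyte is given.
- **Analysis (7.1).** The parameters are AUC and then "maximal amino acid concentration, change from basal to maximal amino acid concentrations, rate to maximal amino acid concentration, and the clearance rate of amino acids", five in all. They "will be assessed with an one-way ANOVA with appropriate post hoc testing", and "Statistical significance will be accepted at an alpha level of p ≤ 0.05". The section ranks none of the five, names no post hoc procedure and makes no adjustment across parameters.
- **Sample size (7.2).** "For peak EAA concentrations previous studies have demonstrated an effect size" of 1.6 (Cohen's d) for healthy young versus incipient sarcopenia, leading to 8 per group at alpha 0.05 and 80% power. The section does not call peak EAA primary, and does not say whether EAA means the sum of the essential amino acids.
- **Hypotheses (2.0).** The first is that "plasma amino acid response will be altered in elderly sarcopenic adults as compared to young and elderly healthy subjects". This has two comparators, but the text does not say whether both must differ, or in which direction. The second is that the "pharmacokinetics of plasma amino acids can be used to distinguish sarcopenic elderly from young and elderly healthy".
- **Analytes (7.3).** The amino acids to be measured are those relevant to the hypothesis; they are not listed.
- **Group sizes (4.0).** Ten completers in each of three groups.

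**The concern.** A plan with an alpha level, a power calculation and a named principal end-point sets out to test a claim. Here the claim is not tied to one parameter, one analyte or one decision rule. After the data are in, several rules would all be consistent with 7.1: any significant ANOVA among the five, a post hoc difference from one comparator, or differences from both. These rules have very different false-positive rates, so the same data could support the first hypothesis under one and fail it under another.

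The contrast matters as much as the parameter. Young versus sarcopenic mixes age with sarcopenia. Only sarcopenic versus healthy elderly separates the two, and 7.2 does not size that contrast.

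**Working it through.** **1. The plan's own figure.** Two-sample t-test, two-sided 0.05, d = 1.6. Noncentrality is d × √(n/2) on 2n − 2 degrees of freedom.
- Solving for 80% power gives n = 7.23, so 8 per group. The stated 8 is reproduced.
- n = 8: noncentrality 1.6 × √4 = 3.2 on 14 df, power 84.5%.
- n = 10: noncentrality 1.6 × √5 = 3.58 on 18 df, power 92.2%.

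Section 7.2 does not state sidedness. The two-sided t-test is the version that returns 8; one-sided gives 6.

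**2. Five ANOVAs, no true effect.** If the five were independent, the chance of at least one p ≤ 0.05 would be 1 − 0.95^5 = 0.226. Summaries of one curve are correlated, so this is only a bound. The documents give no correlation, so equal correlations r are assumed. Simulation used 3 groups of 10, normal outcomes and 40,000 replicates. The last column counts a trial if, on any of the five, the sarcopenic group differs from both others in the same direction by Tukey.

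| r | Any of five ANOVAs significant | Differs from both (Tukey) |
|---|---|---|
| 0 | 22.5% | 1.4% |
| 0.3 | 21.2% | 1.5% |
| 0.5 | 18.7% | 1.3% |
| 0.7 | 15.8% | 1.2% |
| 0.9 | 10.5% | 0.8% |
| 0.95 | 8.7% | 0.6% |

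**3. Pure age effect.** Assume the young differ by 1.6 SD and the two elderly groups are equal, so there is no sarcopenia effect. The table gives the chance that the sarcopenic group differs from both others on any of the five, over r = 0.95 down to 0.

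| | Tukey | Unadjusted t-tests |
|---|---|---|
| Same direction required | 2% to 5% | 4% to 12% |
| Direction not required | about 3% to 8% | 8% to 20% |

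The direction requirement matters here because the first hypothesis in 2.0 speaks only of an altered response.

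**4. One parameter, both contrasts, each at two-sided 0.05, same direction.** Error is 0.9% with no effect and 2.5% under the age effect of step 3. No further adjustment is needed, because both tests must succeed.

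**5. Power for both contrasts.** Young versus sarcopenic is held at 1.6 SD. The sarcopenic versus healthy elderly difference is not in the documents, so two values are assumed. The ranges run from separate t-tests to a pooled error term, with 200,000 replicates and 10 per group.
- Difference also 1.6 SD: 86.8% to 88.4%.
- Difference 0.8 SD: 39.0% to 40.3%.

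**The case against.** The strongest case against is that this is a 30-person first step. Section 2.0 does name the two comparators, and post hoc testing after a three-group ANOVA would ordinarily show both comparisons. Read as requiring both by Tukey, the plan has a no-effect error of only 0.6% to 1.5% even across all five parameters. That is correct, and it limits the harm. But the plan does not state that rule. Post hoc tests can control error across three groups within a parameter; they do not control it across parameters or analytes. The 9% to 16% also rests on assumed equal correlations.

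Three stronger readings are tempting, and the documents do not support them.
- **That 3.0 and 7.2 contradict each other, AUC against peak.** Section 3.0 names no parameter, and the four hours is the sampling window, of which a peak is one feature. The fault is under-specification.
- **That a pure age effect would almost always be reported as support for the hypothesis.** Some ANOVA would nearly always be significant in that case, and rightly so, since the means differ. No section says that the overall ANOVA alone supports 2.0, and 7.1 follows it with post hoc tests.
- **That 1.2 sets a rival, age-only claim.** It says that showing the test "can differentiate between elderly and young populations is a worthwhile first step in developing a new clinical diagnostic test to identify sarcopenia", but this is background rationale and not a hypothesis.

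On analytes, 7.3 refers sample analysis to a cited paper that was not available here. That may settle the laboratory method, but 7.3 itself still leaves the list of amino acids open.

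**Conclusion.** The concern holds as a gap in specification that should be fixed before analysis. No section names one primary parameter, ranks the five, names the post hoc method, adjusts across parameters or says whether both comparators must differ.

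If any significant ANOVA counts, the no-effect error is roughly two to three times the nominal 5% at correlations of 0.95 to 0.7. If both contrasts are required by Tukey, it is well below 5%. Under an age effect alone, the result ranges from 2% to 20% depending on the post hoc method, the direction requirement and the correlation. These figures assume normal outcomes, equal correlations, 10 completers per group and, for the age effect, a difference of 1.6 SD.

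The arithmetic in 7.2 is sound for the one comparison that it covers. It does not cover the whole first hypothesis.

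**What to change.** - **3.0 and 7.1:** name peak plasma EAA within the 4 hours as the single primary parameter, and state whether it is the sum of the EAAs. This keeps the sizing variable of 7.2. If AUC is preferred, 7.2 needs an AUC effect size, which the documents do not give.
- **7.1:** state that the first hypothesis in 2.0 is supported only if the sarcopenic group differs from both the young and the healthy elderly, in the same direction, each at two-sided 0.05, with no further adjustment.
- **7.1:** make the other four parameters secondary, either Holm-adjusted or supportive with confidence intervals; they can inform the second hypothesis. Make individual amino acids exploratory.
- **7.2:** say that the stated 80% power covers only young versus sarcopenic, and add power for both contrasts over a declared range of sarcopenic versus healthy elderly differences.

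**Cost.** Wording in three sections and no extra samples. The other four parameters carry weaker claims. The stated power no longer justifies the sample for the whole first hypothesis: at 10 per group it is about 87% to 88% if the second difference is also 1.6 SD, but 39% to 40% if it is 0.8 SD.

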7.4 Grouping

Subjects in the older groups will be divided into either sarcopenic or non-sarcopenic based on the results of the handgrip assessment at visit 1 and amount of lean tissue derived from the

body composition measurements. The thresholds (per the Sarcopenic Definitions and Outcomes Consortium) are as follows:

Men whose value is < 35.5 kg are considered to have low muscle strength. Women whose value is < 20 kg are considered to have low muscle strength.

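### The one-way ANOVA in 7.1 omits sex; adding it as a main effect is a near-free safeguard for precision and against bias if sex affects the amino acid response

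*Combined protocol and SAP*

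**What the plan says.** Section 7.1 lists five summaries of the plasma amino acid curve (AUC, peak, change from basal to peak, rate to peak, clearance). It states that they "will be assessed with an one-way ANOVA with appropriate post hoc testing", with "Statistical significance will be accepted at an alpha level of p ≤ 0.05". Group is the only factor. No covariate, sex term or sensitivity analysis appears anywhere in the document.

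Sex enters the design in three places:

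- Section 3.0 plans to enrol both sexes, "with a goal to study up to 30 healthy male and females".
- Section 4.0 says "Attempts will be made to balance sexes within groups", with a "goal of 10 completers in each of the three groups". It gives no quota, stratification or matching rule.
- Section 7.4 splits the older subjects by measurement, using lean tissue and sex-specific grip cut-offs: below 35.5 kg for men, and "Women whose value is < 20 kg are considered to have low muscle strength".

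Section 6.0 shows that sex is already recorded for each subject. Section 7.2 bases the sample size on "an effect size (Cohen's D) of 1.6 between health young and individuals with incipient sarcopenia" for peak EAA and arrives at 8 per group. It does not give the sex mix behind that effect size.

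**The concern.** The protocol treats sex as worth balancing and then leaves it out of the analysis. Everyone receives the same 10 g, unscaled to body size, and the endpoints are built from plasma concentrations. A male–female difference is therefore plausible.

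If there is one, two things follow. First, even with a perfect 5:5 split, the sex variance sits in the residual and the precision that balancing could buy is lost. Second, if the groups differ in sex mix, part of the sex difference is counted as a group difference. Randomisation does not protect against this here, because groups are formed by age and by measured muscle status. Nothing makes the share of men below their grip cut-off equal the share of women below theirs. The contrast between sarcopenic and non-sarcopenic older adults, which is central to both hypotheses in Section 2.0, is exposed along with the others.

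**Working it through.** **Inputs from the document.** Three groups of 10 completers (4.0); alpha 0.05, sidedness not stated (7.1); d = 1.6, 80% power, 8 per group (7.2).

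**Assumptions.** Two-sided tests. The size of the sex effect is not in the document, so a range is used. The values d = 1.0 and d = 1.2 are also assumed, because 7.2 gives no effect size for the older-versus-older contrast.

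**1. The plan's own figure.** For a two-sided two-sample t-test at d = 1.6 (noncentral t), power is 0.784 with 7 per group and 0.845 with 8. The stated 8 per group reproduces.

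**2. Scale of the sex effect.** Let δ be the male–female difference in within-sex SDs. With a 5:5 split, the share of within-group variance due to sex is R² = (δ²/4)/(1 + δ²/4), so δ = 2√(R²/(1 − R²)).

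- δ = 0.5: R² = 0.0625/1.0625 = 5.9%
- δ = 1.0: R² = 0.25/1.25 = 20%
- δ = 1.63: R² = 40%

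**3. Error inflation under perfect balance.** The expected mean square error without sex is 1 + δ² × (30 × 0.25)/27. It rises by 7% at δ = 0.5, 18% at 0.8 and 28% at 1.0. The unadjusted test is then conservative: simulated pairwise type I error is 0.043, 0.034 and 0.028.

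**4. Pairwise power, 10 per group, unadjusted alpha 0.05.** Without sex, the noncentral t has 27 df and noncentrality d√(10/2). With sex, it has 26 df and d is replaced by d/√(1 − R²). Here d is on the total within-group SD.

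| d | Without sex | With sex, R² = 0 | 5.9% | 20% | 40% |
|---|---|---|---|---|---|
| 1.0 (assumed) | 58% | 58% | 60% | 67% | 79% |
| 1.2 (assumed) | 73% | 73% | 76% | 82% | 92% |
| 1.6 (planned) | 93% | 93% | 94% | 97% | 99% |

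At R² = 5.9% the gains are 57.8% to 60.2%, 73.5% to 75.9% and 93.2% to 94.4%. At R² = 0 the loss is about 0.1 points.

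This formula slightly overstates the gain when the split is exactly 5:5. For d = 1.6 and δ = 1.0, simulation gives 0.948 without sex and 0.971 with it. If d = 1.6 refers instead to the within-sex SD, power without sex is 0.922, 0.906 and 0.890 at δ = 0.5, 0.8 and 1.0, against 0.931 with sex.

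**5. Bias under unequal mix.** Bias = (difference in proportion of men) × δ.

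- 7/3 vs 4/6 (men/women): 0.3 × 0.5 = 0.15; 0.3 × 1.0 = 0.30; 0.3 × 1.63 = 0.49 SD.
- 7/3 vs 3/7: 0.4 × 0.5 = 0.20; 0.4 × 0.8 = 0.32; 0.4 × 1.0 = 0.40 SD.

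Simulated pairwise type I error of the one-way analysis at nominal 0.05:

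| Split | Sex differences δ | Type I error |
|---|---|---|
| 6/4 vs 4/6 | 0.5, 0.8, 1.0 | 0.048, 0.046, 0.044 |
| 7/3 vs 4/6 | 0.5, 1.0, 1.63 | 0.053, 0.064, 0.070 |
| 7/3 vs 3/7 | 0.5, 0.8, 1.0 | 0.065, 0.082, 0.095 |

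With sex in the model, type I error is about 0.05.

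**6. How likely is imbalance?** If sex were a coin flip (an assumption; the stated aim should do better), two groups of 10 would differ by at least 3 men with probability 0.26 and by at least 4 with probability 0.115.

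**The case against.** The case for leaving 7.1 alone has force.

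- No passage gives a male–female difference for any of the five endpoints. The fixed dose makes one plausible, no more. This stands, and it makes every consequence above conditional.
- At the plan's own d = 1.6, pairwise power is already about 93% without sex. If the SD behind that effect size came from a mixed-sex sample, sex variance is already in the planned power, and adjustment is a gain rather than a repair. This also stands. However, d = 1.6 is for peak EAA in healthy young versus incipient sarcopenia, and nothing shows that it carries over to the older-versus-older contrast.
- The design already attends to sex. At 6/4 vs 4/6 the type I error stays below 0.05, and at 7/3 vs 4/6 it reaches only 0.05–0.07. Marked inflation needs a larger imbalance together with a sizeable sex effect. This stands, but balance is only attempted, and balance alone does not take the sex variance out of the residual.
- A main-effects model assumes the same sex difference in all three groups, which about five subjects per cell cannot check. That is a genuine limit of the remedy.

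A reader might go further and infer that sex differences do inflate the error here, that any imbalance invalidates the comparisons, or that the sex-specific grip cut-offs will produce unequal groups. The documents support none of these. They do not size a sex effect, small imbalances do not raise the type I error, and sex-specific cut-offs allow the older groups to differ in sex mix without showing that they will.

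**Conclusion.** The point holds as a conditional one. The analysis omits a variable that the protocol tries to balance in non-randomised groups, and including it costs almost nothing. The benefit ranges from nil (sex has no effect) through 1–2.5 power points (sex explains about 6% of within-group variance) to about 21 points at d = 1.0 (sex explains 40%). Protection against bias matters more than power at the planned effect size: at 7/3 vs 3/7, type I error would otherwise be 0.065–0.095 for sex differences of 0.5–1.0 SD.

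These figures assume 10 completers per group, two-sided unadjusted alpha of 0.05, a common sex difference across groups, and effect sizes of 1.0 and 1.2 that are not in the plan. One-way ANOVA is a defensible choice. This is an inexpensive improvement and not a demonstrated error; it gives no reason to change the sample size.

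**What to change.** In 7.1, replace the one-way ANOVA with a linear model containing group and sex as main effects. Report sex-adjusted group means and pairwise contrasts for each endpoint, together with the number of men and women in each group. Specifying this before analysis also removes the temptation to decide on adjustment after seeing the data.

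The cost is a change of wording, since sex is already recorded. It uses one residual degree of freedom (27 to 26). Under imbalance, the collinearity of group and sex widens the contrast SE slightly, by about 3% at 7/3 vs 4/6. The report should state that the model assumes a common sex difference across groups and that the study is too small to test it.
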